6.2.4 Dosage Adjustments, Delays, Rules for Withholding or Restarting, Permanent Discontinuation

6.2.4.1 AMG 596

Dose Delay or Dose Reduction

Any clinically relevant (as determined by the investigator) grade 4 adverse event related to IP that does not meet the DLT criteria should lead to a dose delay and/or a dose reduction. The decision if a dose delay or reduction will be performed is up to the investigator's discretion. The sponsor may be consulted.

In addition, cytokine release syndrome of \geq grade 3 ([Appendix E](#)) should lead to dosing interruption and treatment with immunosuppressive therapies should be performed (see [Section 6.3](#) for details).

In case of re-appearance of the same grade 4 adverse event, IP should be permanently discontinued.

For persistent or re-occurring clinically relevant grade 3 adverse event related to IP, a dose delay or a dose reduction should be considered.

Infusion Interruption

Significant events requiring a change in treatment will be managed by immediate infusion interruption and should be documented in source documents and in the eCRF:

- The subject experiences a DLT as defined in [Section 6.2.3](#).
- The subject experiences a clinically relevant grade 4 adverse event related to IP (see above)
- The subject meets criteria for discontinuation of IP as described in [Section 8.3](#)
- Technical problem with the infusion pump
- The investigational product is incorrectly prepared or administered (eg, overdose)

Restarting the Infusion

Treatment may resume if the interruption is \leq 21 days:

- If the interruption occurred due to other reasons than toxicity (technical or logistic reasons; eg, diagnostic measurements). The infusion can be restarted at the same dose and without additional measures or delays.
- The toxicity has resolved to \leq grade 1. The infusion can be restarted according to guidelines presented in [Table 3](#) and [Table 4](#). Non-hematological Criteria for Dose Reduction.
- The toxicity occurred during the DLT period and has resolved to grade 2. The infusion can only be restarted in an individual subject with a clear clinical benefit from treatment after consultation with the sponsor on a case-by-case basis.

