Restarting the infusion after a treatment interruption requires care and should be performed in the clinic/hospital under the supervision of the investigator or designee and the subject should be hospitalized for a minimum of 24 hours when the infusion interruption meets the following criteria:

- associated to an AE, or
- interruption > 24 hours due to a pump related issue.

The restart should be performed in the hospital with all infusion day 1 specific measures if the reason for the interruption was other than a technical issue (eg, pump related

issue) or the interruption was > 24 hours independent of reason. Prophylactic treatment with steroid (eg, dexamethasone) is mandated before restarting of AMG 596. If step-dosing was already performed at the start of a cycle, the infusion should be restarted with step-dosing again if the infusion interruption was [REDACTED].

Subjects in [REDACTED] that have a treatment interruption during cycle 1 should be allowed to complete a total of [REDACTED] infusion, and subjects in [REDACTED] cycles that have a treatment interruption during cycle 1 should be given the opportunity to complete a total of [REDACTED] of infusion even though these may not be DLT evaluable subjects. Replacement of subjects in [REDACTED] off schedule cohorts that have a treatment interruption during cycle 1 will require discussion on a case by case basis between sponsor and investigator.

Restart after an interruption lasting [REDACTED] may be allowed after careful risk-benefit evaluation and requires discussion between investigator and sponsor. Hematological criteria for dose reduction are presented in Table 3 and non-hematological criteria are presented in Table 4. Dose reduction is possible with re-treatment at 1 dose level lower (Section 6.2.4.1)

Table 3. Hematological Criteria for Dose Reduction

| CTCAE Grade | ANC (10 ⁹ /L) | Platelets (10 ⁹ /L) | Dose Delay ^a | Dose Reduction |
|---------------|--------------------------|--------------------------------|--|---|
| Hematological | | | | |
| 0-2 | > 1.0 | > 50 | Continue infusion | No change |
| 3 | < 1.0 – 0.5 | < 50 – 25 | Continue infusion until Investigator assesses toxicity to require interruption | No change |
| 4 | < 0.5 | < 25 | Delay until ≤ grade 2 | Restart at 1 dose level lower, consider re-escalation if completely recovered to baseline and no new toxicity occurred within 7 days of infusion. |

Approved

Table 4. Non-hematological Criteria for Dose Reduction

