| CTCAE Grade* | Dose Delay | Dose Reduction | Comment |
|---|-----------------------|---|---|
| Non-hematological | | | |
| Cytokine release syndrome, tumor lysis syndrome, acute kidney injury | | | |
| 2 | Delay until ≤ grade 1 | No change | Restart in hospital |
| 3 | Delay until ≤ grade 1 | Restart at 1 dose level lower | Consider re-escalation if completely recovered and no new toxicity occurred within 7 days of infusion. Permanent discontinuation of study treatment if no recovery within 21 days. Start at the same dose if resolved cytokine release syndrome, infection, tumor lysis syndrome, or hypoxia. |
| 4 | Discontinue infusion | Permanent discontinuation of study treatment | - |
| All other non-hematological toxicities and clinically significant laboratory parameters | | | |
| 0-2 | Continue infusion | No change | Interruption can be considered if deemed necessary by the investigator |
| 3 | Delay until ≤ grade 2 | Resolution to grade 1 or 2: Restart at 1 dose level lower Resolution to normal within 1 week or a relationship to study drug can be ruled out: No change | Per the Investigator medical discretion to decide whether to continue the infusion for up to 72 hours if the toxicity or abnormal labs are responding to treatment or represents an asymptomatic laboratory change. Permanent discontinuation of study treatment if no recovery within 21 days |
| 4 | Discontinue infusion | Permanent discontinuation of study treatment | - |

ANC = Absolute neutrophil count; CTCAE = Common terminology criteria for adverse events;

DLT = Dose-limiting toxicity

^a Applies to all hematologic toxicity that persists for > 24 hours despite appropriate treatment

* For CRS criteria defined in [Appendix E](#) apply

Approved

6.2.4.2 AMG 404

Dose Delay or Dose Reduction

Each subject will stay on the dose level assigned until treatment needs to be stopped. The reason for dose withholds and dose delays is to be recorded on each subject's CRF. Specific guidance for management of adverse events associated with AMG 404 are provided in [Appendix G](#)

Immune-related Adverse Reactions

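### For a DLT that recovers only to grade 2, Sections 6.2.4.1 and 6.2.5 give different restart rules, and no general text says which governs

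*Protocol*

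**What the plan says.** **Section 6.2.4.1, interruption.** "Significant events requiring a change in treatment will be managed by immediate infusion interruption". A DLT heads the list of such events; clinically relevant related grade 4 events form a separate item.

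**Section 6.2.4.1, restart.** The list opens "Treatment may resume if the interruption is" at most 21 days. Its second bullet covers toxicity that has resolved to at most "grade 1. The infusion can be restarted according to guidelines presented in" Tables 3 and 4. Its third bullet covers toxicity that arose in the DLT period and stands at grade 2: restart is possible only for an individual subject who is clearly benefiting, after consulting the sponsor, case by case.

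**Table 3, grade 4 row.** "Delay until ≤ grade 2", then "Restart at 1 dose level lower, consider re-escalation if completely recovered to baseline". The footnote to the delay column reads "Applies to all hematologic toxicity that persists for > 24 hours despite appropriate treatment".

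**Table 3, grade 3 row.** "Continue infusion until Investigator assesses toxicity to require interruption".

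**Table 4, grade 3 row for events without a row of their own.** The same delay rule as the Table 3 grade 4 row, then "Resolution to grade 1 or 2: Restart at 1 dose level lower". Treatment stops permanently if there is no recovery within 21 days.

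**Section 6.2.5.** A DLT ends treatment permanently unless it improves to grade 1 or lower, or to baseline, within 14 days; the investigator sees clinical benefit; the investigator and medical monitor agree; and the subject is willing. The first bullet of the same section sends the reader to Section 6.2.3 for the exemption.

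**The concern.** A subject has a DLT, the infusion is stopped, and the event settles at grade 2. A site reading 6.2.4.1 can discuss a restart with the sponsor. A site reading Table 4 can restart one level lower. A site reading 6.2.5 must stop for good. The drug is a first-in-human T-cell engager given at about 12 or more sites, so the same clinical picture could lead to re-exposure at one site and withdrawal at another. The table of adverse events leading to withdrawal from investigational product (Protocol 10.5.2; SAP 9.6.1) would partly reflect which rule each site followed.

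**Working it through.** No arithmetic applies; the check is a comparison of texts.

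**Step 1. Can a DLT fall under each rule?** Section 6.2.3 makes a related grade 3 non-hematological event a DLT if it lasts more than 3 days despite treatment, so such events reach the residual Table 4 grade 3 row. Several are removed by stricter rules: CRS, tumor lysis and acute kidney injury have their own rows requiring grade 1 or lower; neurologic events fall under Table 5 and 6.2.5; liver events meeting 6.3.4 stop permanently. Grade 4 non-hematological events also stop permanently. The Table 4 conflict concerns what remains. On the hematological side, ANC below 0.5 × 10⁹/L for at least 7 days and platelets below 25 × 10⁹/L for more than 7 days are DLTs that sit in the Table 3 grade 4 row.

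**Step 2. What does each rule say at grade 2?**

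| Rule | Outcome at grade 2 | Addresses DLTs by name? |
|---|---|---|
| 6.2.4.1, third restart bullet | Restart possible, case by case | No; it refers to toxicity in the DLT period |
| Table 4, residual grade 3 row | Restart one level lower | No exclusion |
| Table 3, grade 4 row | Restart one level lower | No exclusion in the table, but see the objection |
| 6.2.5 | Permanent discontinuation | Yes |

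**Step 3. Does the baseline alternative in 6.2.5 remove the conflict?** Only if the subject's baseline was itself at that level. For counts, inclusion criterion 110 requires ANC above 1.5 and platelets above 100 × 10⁹/L, while Table 3 treats ANC just above 1.0 and platelets just above 50 as grade 2 or lower. A subject whose pre-dose counts still met eligibility has not returned to baseline at those values.

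**Step 4. Is precedence stated anywhere?** The first 6.2.5 bullet points to 6.2.3, which defines DLTs and has no restart exemption; the criteria are at the end of the 6.2.5 list itself. The interruption list in 6.2.4.1 points to 8.3 for discontinuation, not to 6.2.5. Section 6.3.6 bars rechallenge for anyone clearly meeting the 6.2.5 criteria, but it belongs to the hepatotoxicity rules. No general statement exists.

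**Step 5. Two secondary mismatches.** Related platelets of 25–50 × 10⁹/L for more than 7 days are a DLT, so 6.2.4.1 makes interruption mandatory and immediate; the Table 3 grade 3 row leaves interruption to the investigator. For toxicity in general, the second restart bullet brings in the tables at grade 1 or lower, while the two rows above are written for recovery to grade 2 or lower.

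**The case against.** The strongest reply is that 6.2.5 is the only restart rule triggered by a DLT as such, that it is mandatory, and that the specific rule should prevail over general grade-based tables. Section 6.3.6 takes that view for liver events. This is probably what the sponsor intends: the Amendment 4 rationale lists aligning treatment discontinuation with DLTs. It remains an inference, because outside hepatotoxicity the protocol does not say so, and the section's own pointer sends a site to the wrong place.

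A second reply limits the role of the tables. Section 6.2.4.1 opens by directing dose delay or reduction for clinically relevant related grade 4 events that are not DLTs, and its second restart bullet invokes the tables only at grade 1 or lower. A reader might infer that Tables 3 and 4 simply restart any DLT at grade 2; read with this text, they do not. The opening sentence weakens the Table 3 grade 4 case, even though the table's footnote covers all persistent hematologic toxicity. It does not reach grade 3 events, so the Table 4 row stands without a DLT exclusion. Nor does it touch the third restart bullet.

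A third reply is that the third bullet and 6.2.5 both require clinical benefit and sponsor-side involvement. That narrows the practical gap but does not close it: at grade 2 one permits a restart and the other forbids it.

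On platelets, a reader might infer that a DLT is told both to continue and to interrupt. The Table 3 cell says to continue only until the investigator finds interruption necessary, so the difference is between mandatory and discretionary interruption.

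**Conclusion.** The inconsistency is real and should be corrected. The clearest conflict is between the third restart bullet of 6.2.4.1, together with the residual Table 4 grade 3 row, and Section 6.2.5; the Table 3 grade 4 row belongs to it less clearly. The conclusion assumes that toxicity in the third bullet includes DLTs. That is the natural reading, since DLTs head the interruption list just before it, but it is not explicit.

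Its size cannot be put as a number, because the documents give no rate for DLTs that recover only to grade 2. It is tempting to subtract 14 days from 21, or the Table 3 restart counts from the eligibility minimum, but neither measures the disagreement. The 21 days in 6.2.4.1 cap the length of an interruption, the 14 days in 6.2.5 limit the time to improve, and both can be met together. The 21-day recovery limit in Table 4 is closer in kind, but the conflict at grade 2 exists whatever the timing. Eligibility counts are not the 6.2.5 test, which is grade 1 or the subject's own baseline.

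A reader might also infer harm to the dose-escalation results. The documents do not support that: the event is already a DLT whether or not the subject restarts, so DLT counts and the inputs to the Bayesian logistic regression model are unchanged. The consequences are for subject safety, site consistency and the tabulated withdrawals.

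**What to change.** 1. Add a footnote to Tables 3 and 4: any event meeting the 6.2.3 DLT definition is interrupted immediately and may restart only if all the DLT criteria in 6.2.5 are met; stricter event-specific rules still apply (Table 4 grade 4, Appendix E for CRS, Table 5, Section 6.3.4, and the neurologic and kidney-injury bullets of 6.2.5). This also settles the platelet mismatch.
2. Limit the third restart bullet of 6.2.4.1 to DLT-period toxicity that is not a DLT.
3. Point the first bullet of 6.2.5 to the DLT criteria in the same list instead of to 6.2.3.
4. For non-DLT toxicity, have the tables and 6.2.4.1 state one restart grade. Which grade is the sponsor's clinical decision.

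The cost is a footnote, edits to bullets in 6.2.4.1 and one cross-reference at the next amendment, plus table wording if the sponsor changes the grade there. No new data or visits are needed.

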6.2.5 Permanent Discontinuation

A subject will permanently discontinue treatment with investigational products in the event of:

- Dose-limiting or other unmanageable toxicity. For exemption, please see [Section 6.2.3](#)).
- Clinically significant disease progression or deterioration.
- Occurrence of neurologic-related adverse event considered related to AMG 596 and/or AMG 404 by the investigator and meeting one or more of the following criteria:
 - Grade 3 seizure, ataxia or encephalopathy
 - A neurologic-related adverse event CTCAE grade 4
 - A neurologic-related adverse event leading to treatment interruption that needed more than 1 week to resolve to CTCAE grade ≤ 1
- Occurrence of acute kidney injury considered related to AMG 596 and/or AMG 404 by the investigator and meeting one or more of the following criteria:
 - Creatinine $> 3x$ baseline or > 4.0 mg/dL and not recovered to CTCAE grade 1 or ≤ 0.3 mg/dL within 21 days
 - Hemodialysis required
- Subject's request
- Subject or investigator not compliant with the study protocol
- Occurrence or progression of a medical condition which, in the opinion of the investigator after medical consideration, is not associated with the disease under study and should preclude further participation of the subject in the study
- Pregnancy
- A DLT leads to permanent discontinuation unless the following criteria apply, in which case a restart of treatment at the same or a lower dose may be allowed:
 - The AE (including relevant lab values) is reversible and improves to grade ≤ 1 or baseline within 14 days
 - The patient is experiencing clinical benefit as assessed by the investigator
 - There is agreement between the investigator and the Amgen Medical Monitor that treatment may be restarted
 - The subject is willing to continue treatment after the investigator has led an appropriate discussion of potential risks and benefits with the subject

All reasons for treatment discontinuation should be clearly and concisely documented in the eCRF. If a subject has not continued to present for study visits, the investigator should determine the reason and circumstances as completely and accurately as possible.

In any case of premature treatment discontinuation, the investigator should make every effort to perform all examinations scheduled for the end of treatment (EOT) and safety

follow up (SFUP) visits. These data should be recorded, as they comprise an essential evaluation that should be performed prior to discharging any subject from the study and to allow for the evaluation of the study endpoints.

6.3 Specific Recommendations for Cytokine Release Syndrome, Neurologic Events and Hepatotoxicity

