6.3.2 Infusion Interruption/Dose Modification due to Neurologic Events

Patients with glioblastoma or malignant glioma may present with generalized symptoms (eg, headaches, cognition and personality changes) and focal signs (eg, hemiparesis, sensory loss, visual field disturbances) (Omuro and DeAngelis, 2013).

Recommendations for management, including interventions and infusion interruptions for neurologic-related adverse events, are presented in Table 5. As neurologic events may be anticipated in the study population, guidance regarding reporting of safety events, including disease-related and adverse events, is provided in Section 9 (Safety Data Collection, Recording, and Reporting).

Table 5. Management of Neurologic Events (by Severity)

| CTCAE Grade | Intervention | Instructions for Infusion Interruption or Permanent Discontinuation |
|-------------|--|---|
| 3 | 
Perform physical exam, assess vital signs and conduct safety laboratory tests
 
Depending on the nature of the adverse event, additional measures (eg, CSF investigations, contrast-enhanced MRI of the head) can be taken upon discretion of the investigator
 
MRI should also be considered for subjects who permanently discontinue treatment at the discretion of investigator
 | 
Immediately interrupt AMG 596
 
Restart AMG 596 infusion within 2 weeks, but not earlier than 72 hours (3 days) after the infusion has stopped, if the event resolves to grade ≤ 1 within 7 days
 
Delay AMG 404 dosing until day 8 after AMG 596 restart if AMG 404 dosing was scheduled during interruption
 
Permanently discontinue AMG 596 and AMG 404 if considered by the investigator related to study drug and if there is no improvement to grade ≤ 1 within 7 days
 |
| 4 | 
Perform physical exam, assess vital signs and conduct safety laboratory tests
 
Depending on the nature of the adverse event, additional measures (eg, CSF investigations, contrast-enhanced MRI of the head) can be taken upon discretion of the investigator
 
Conduct MRI for subjects who permanently discontinue treatment
 | 
Immediately interrupt AMG 596
 
Permanently discontinue AMG 596 and AMG 404
 |

CSF – cerebrospinal fluid, CTCAE – Common Terminology Criteria for Adverse Events, MRI – magnetic resonance imaging

For subjects who experience serious neurologic adverse events leading to treatment interruption, if the event has decreased to at least CTCAE grade 1 within 1 week,

Approved

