treatment may be restarted within 2 weeks, but not earlier than 72 hours (3 days) after the infusion was stopped.

Seizure

If the neurologic event was a seizure (CTCAE grade 2 or above), appropriate prophylactic anticonvulsant treatment (a therapeutic dose of eg, phenytoin or levetiracetam) can be administered during the next treatment cycle. In case of occurrence of seizure grade 3, the investigational products will have to be stopped immediately and treatment will be permanently discontinued, and investigations associated with and previously described for a CTCAE grade 3 or higher neurologic-related adverse events, must also be performed.

Depressed level of consciousness

Depressed level of consciousness is a common neurological sign of intracranial pressure increase. AMG 596 may cause inflammation at the site of the tumor, leading to worsening of increased intracranial pressure resulting in neurological toxicity including a depressed level of consciousness.

Prophylactic use of corticosteroids is mandated for any subject receiving a new cycle of AMG 596 (████████████████████), with dexamethasone 8 mg IV (or equivalent dose of other corticosteroids) given within 1 hour prior to administration of AMG 596 and the second dose of dexamethasone 8 mg IV given 12 hours after start of the infusion, and subsequent tapering at the discretion of the investigator. Prophylactic treatment with steroid (eg, dexamethasone) is also mandated before restarting of AMG 596 or otherwise clinically indicated (see [Section 6.3](#)).

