6.3.6 Criteria for Rechallenge of Amgen Investigational Product After Potential Hepatotoxicity

The decision to rechallenge the subject should be discussed and agreed upon unanimously by the subject and investigator, after consultation with Sponsor.

If signs or symptoms recur with rechallenge, then the investigational products should be permanently discontinued. Subjects who clearly meet the criteria for permanent discontinuation (as described in [Section 6.2.5](#)) should never be rechallenged.

Approved

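### For a related, non-DLT grade 3 ataxia or encephalopathy that falls to grade ≤ 1 within 7 days, Protocol 6.2.5 requires a permanent stop while Table 5 instructs a restart

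*Protocol*

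**What the plan says.** Protocol Section 6.2.5 is a mandatory list of reasons for permanently stopping the investigational products. For a neurologic event that the investigator judges related to AMG 596 and/or AMG 404, one sufficient reason is "Grade 3 seizure, ataxia or encephalopathy". No recovery condition is attached. Grade 4 events, and events that take more than a week to reach grade ≤ 1 after an interruption, are separate alternatives.

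Table 5 in Section 6.3.2 has one row for all grade 3 neurologic events. AMG 596 is interrupted at once. Then: "Restart AMG 596 infusion within 2 weeks, but not earlier than 72 hours (3 days) after the infusion has stopped", provided the event reaches grade ≤ 1 within 7 days. The row stops both products permanently only if the event is related and has not improved that far in 7 days. The next paragraph covers serious neurologic events that led to an interruption: "if the event has decreased to at least CTCAE grade 1 within 1 week", "treatment may be restarted within 2 weeks, but not earlier than 72 hours (3 days) after the infusion was stopped".

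The one exception in Section 6.3.2 is for seizure: "In case of occurrence of seizure grade 3, the investigational products will have to be stopped immediately and treatment will be permanently discontinued". The section names neither ataxia nor encephalopathy.

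Section 6.2.3 makes the same three grade 3 events DLTs when they are related and fall within the DLT period. The DLRT can also declare a later event a DLT by unanimous decision. The last bullet of 6.2.5 lets a subject with a DLT restart if four conditions are met.

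**The concern.** This is a subject-level safety stopping rule in a first-in-human study, and Table 1 lists neurologic events as a potential risk of AMG 596. A site managing such an event would naturally turn to the neurologic table. Following it would re-dose a subject whom 6.2.5 removes from treatment. In Arm 2, AMG 404 could resume as well, because the same row only delays an AMG 404 dose that fell due during the interruption. A site that follows 6.2.5 instead would depart from the Table 5 instruction. The seizure exception makes matters worse: naming one of the three events invites the inference that the other two stay under the table.

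**Working it through.** No figure in the plan needs reproducing, so the check sets the rules side by side. The test case is a grade 3 ataxia or encephalopathy, judged related, at grade ≤ 1 by day 7.

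| Rule | Applies? | Action |
|---|---|---|
| 6.2.5, neurologic criteria | Yes | Permanent stop, both products |
| 6.3.2, Table 5, grade 3 row | Yes | Restart AMG 596 |
| 6.3.2, paragraph after Table 5 | Yes, if serious | Restart permitted |
| 6.3.2, seizure paragraph | No | None |
| 6.2.5, last bullet | Only if a DLT | Restart possible under four conditions |

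1. *Coverage of the exception.* 6.2.5 names 3 grade 3 events and 6.3.2 excepts 1 of them (seizure). 3 − 1 = 2 have no exception.

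2. *Event not a DLT* (outside the DLT period and not declared a DLT by the DLRT). The last bullet of 6.2.5 does not apply. 6.2.5 gives stop and Table 5 gives restart, with nothing to qualify either.

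3. *Event a DLT.* The last bullet of 6.2.5 sets 4 conditions: recovery to grade ≤ 1 or baseline within 14 days, clinical benefit, agreement between investigator and Medical Monitor, and a willing subject. Table 5 sets a recovery condition (7 days) and no other. 4 − 1 = 3 conditions are missing from Table 5. The text does not say whether this bullet overrides the neurologic criteria in the same list.

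4. *Cases with no conflict.* A related event not at grade ≤ 1 within 7 days meets a stopping criterion in both places. Unrelated events, and other grade 3 neurologic events that recover in time, may restart under both. Grade 3 seizure is stopped by 6.3.2 itself.

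5. *Restart window.* Table 5 runs from day 3 to day 14 after the stop, so 14 − 3 = 11 days at most. Recovery must come first: an event that recovers on day 7 after the stop leaves 14 − 7 = 7 days.

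**The case against.** The best answer is that a conservative reading exists. 6.2.5 is worded as an obligation. Section 6.3 is headed as recommendations, Table 5 is introduced in the same terms, and the paragraph after it only permits restart. A permission gives way to a mandatory stop, so that paragraph need not contradict 6.2.5. This stands for the paragraph, and it means that sites are not left without a safe course. It does not dispose of the table. The grade 3 cell is an imperative, its column is headed as instructions, and it states its own narrower stopping rule for related events. No sentence says which section prevails.

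A second answer is Section 6.3.6, where "Subjects who clearly meet the criteria for permanent discontinuation" in 6.2.5 are barred from rechallenge. The sentence cites the general list, which contains no liver-specific criterion, so it lends some support to reading 6.2.5 as absolute. But it belongs to the hepatotoxicity rechallenge rules and does not settle the neurologic case.

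A third is that safeguards exist. Restart after an adverse event is supervised, with at least 24 hours in hospital and mandated steroid prophylaxis (6.2.4.1). These govern how a subject is re-dosed. They do not carry out a stop.

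A reader might infer a second conflict from Table 4. Its general grade 3 row says "Resolution to grade 1 or 2: Restart at 1 dose level lower", and the restart rule in 6.2.4.1 leads there: "The infusion can be restarted according to guidelines presented in" Tables 3 and 4. The inference is weak. Table 4 differs from Table 5 for every grade 3 neurologic event, because it accepts recovery to grade 2. The sensible reading is that the specific neurologic table displaces the general one.

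**Conclusion.** The protocol is wrong as written, as an internal inconsistency in a safety stopping rule. The flat contradiction is confined to a related grade 3 ataxia or encephalopathy that reaches grade ≤ 1 within 7 days and is not a DLT: 2 of the 3 events named in 6.2.5. For a DLT the gap is smaller. Both sections may lead to restart, but Table 5 omits 3 of the 4 conditions in 6.2.5.

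Three stronger readings are not supported. The first is that stop and restart collide for every such event; the DLT bullet prevents that conclusion within the DLT period. The second is that the whole grade 3 row is unsafe; it agrees with 6.2.5 for unrelated events and for other neurologic events that recover in time. The third is that a known number of subjects, or a fixed 11 days of exposure to re-dosing, is at issue; the documents give no event frequency, and 11 days is only the longest possible window.

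The conclusion assumes that the investigator judges the event related and that no precedence rule exists outside these documents. Endpoints, sample size and analysis are unaffected.

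**What to change.** Settle the open question first, then align the text.

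1. The sponsor decides, and states in 6.2.5, whether the DLT restart exception applies to events that meet the neurologic criteria in the same list. The documents do not settle this. Writing an unconditional stop into Table 5 beforehand could create a new conflict.

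2. Add to the Table 5 grade 3 row and to the paragraph after it: *Exception: a related grade 3 seizure, ataxia or encephalopathy is not restarted under this table. Section 6.2.5 governs: permanent discontinuation, unless 6.2.5 states that its DLT exception applies.*

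3. Extend the seizure paragraph of 6.3.2 to related grade 3 ataxia and encephalopathy, with the same deference to 6.2.5.

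The row itself should stay, since it is right for the other events. A cross-reference from Table 4 to 6.2.5 is optional. The cost is negligible: one decision and a few lines of amended wording, with no change to design, sample size or analysis.
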